## **Statistical Analysis Plan**

Analyses of variance (ANOVA) will be conducted to examine differences in outcomes measures across the three subject groups with normal hearing (NH), sensorineural hearing loss (SNHL), and middle ear disorders (ME). Bonferroni corrections will be applied for multiple comparisons. T-tests will be used to examine effects of method (clinical vs. experimental wideband) within each subject group.

For the Primary Outcome measure of Middle Ear Test, separate ANOVAs will be used to examine differences across groups within each method. In the first ANOVA, the independent variable will be subject group, and the dependent variable will be clinical tympanometric peak static acoustic admittance at 226 Hz. In the second ANOVA, the independent variable will be subject group, and the dependent variable will be wideband absorbance at ambient pressure averaged across half-octaves from 250 to 8000 Hz.

For the Secondary Outcome measure of Middle Ear Muscle Reflex Test, separate t-tests will be used to examine the difference in middle ear muscle reflex threshold between the clinical and wideband experimental methods within each subject group.

For the Secondary Outcome measure of Wideband Otoacoustic Emission Test, an ANOVA will be used to examine the differences across subject groups in transient evoked otoacoustic emission (TEOAE) signal-to-noise ratio (SNR) (averaged across half-octave bands from 1000 to 8000 Hz).

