Official Title: Comprehensive Wide Bandwidth Test Battery of Auditory Function
in Veterans

NCT Number: 02019888

Document Date: 3/5/2021

Study Protocol

The goal of this research is to evaluate a comprehensive test battery of new wide-bandwidth, i.e., wideband (WB), acoustical tests of auditory function in the differential diagnosis of middle ear, cochlear and neural pathologies in a population of Veterans. WB tests refer to ear canal tests using sound responses measured from 200 Hz to frequencies as high as 8000 Hz, a bandwidth that is critical for speech perception. There will be tests in the battery for middle-ear assessment using absorbance cochlear assessment using otoacoustic emissions (OAEs) and the acoustic stapedius reflex (ASR) using middle ear power absorption. Results will be compared with a standard single-frequency clinical immittance test battery routinely used in the assessment of auditory function in Veterans.

Aim 1 seeks to evaluate the accuracy of the WB test battery in the differential diagnosis of middle-ear pathology and related conductive hearing loss by comparing the sensitivity and specificity of the WB battery to the traditional immittance battery for disorders common in Veterans including tympanic membrane perforation and serous otitis media. Aim 2 seeks to modify a WB ASR test to provide automatic detection of the ASR threshold for comparison with the traditional single-frequency ASR threshold. Aim 3 seeks to validate the use of Transient-evoked otoacoustic emission (TEOAE) and spontaneous otoacoustic emissions (SOAEs) tests in Veterans to assess cochlear status, and evaluate their test performance in classifying ears with normal hearing and sensorineural hearing loss. The combination of tests across aims will allow for examination of the diagnostic accuracy of the full WB test battery in comparison to the single-frequency admittance test battery to detect any type of hearing loss including sensorineural, conductive and mixed. The hypothesis is that the WB test battery is more accurate than the traditional immittance test battery in identifying ears with normal auditory status and ears with a range of risks for auditory pathology.

Methods:

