Subjects- Human subjects will be recruited for this study who have had a hearing evaluation from the VA Audiology Service at the Portland VA Medical Center and the H. Quillen VA Medical Center. These subjects will respond to flyers or be contacted from an IRB-approved human subject volunteer registry. Data will be acquired from three groups of subjects with normal hearing, sensorineural hearing loss (SNHL), and middle ear disorders.

Testing- All subjects will receive the same clinical and WB test battery. Each subject will be tested in one laboratory visit. Subjects will be enrolled in this study that upon otoscopic inspection of their ear canals, have no active drainage from the ears, and have ear canals free of cerumen (wax) impaction, bilaterally. Subjects who are found to have draining ears or cerumen impaction will be referred for treatment. These individuals may be enrolled in the study following successful treatment for their conditions. All subjects will have a standard pure-tone air- and bone-conduction

audiogram while comfortably seated in a sound-treated booth. Standard insert earphones and a bone-conduction vibrator will be used to present the sound stimuli. Next, speech audiometry will be completed and the speech reception thresholds, uncomfortable loudness test for speech, and speech recognition scores will be obtained. Then the subjects will have a standard immittance test battery consisting of a tympanogram and acoustic reflex threshold testing. Stimuli will not exceed a level of 100 decibels hearing level (dB HL). Finally, the wideband test battery will be performed with adults seated comfortably in a sound-treated booth. A small probe with a soft rubber tip will be inserted in the subject's ear canal, and the subject will be asked to remain quiet while sounds are presented to an ear via sound sources within the probe. Responses will be measured using a miniature microphone within the probe. The tests in the wideband battery are similar to the clinical admittance battery and include ambient absorbance, absorbance tympanometry and acoustic reflex threshold. The otoacoustic emission testing is a separate measurement of inner ear function typically conducted in the clinic using different equipment.

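### The SAP plans plain ANOVA with no provision for unequal variances. If the middle-ear group is the more variable one, the F test and any pooled-error pairwise tests are miscalibrated in a direction set by unstated group sizes.

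*SAP*

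**What the plan says.** The first paragraph of the SAP sets the general method: "Analyses of variance (ANOVA) will be conducted to examine differences in outcomes measures across the three subject groups". The only refinement is "Bonferroni corrections will be applied for multiple comparisons".

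The SAP then applies ANOVA three times. In the first primary analysis "the dependent variable will be clinical tympanometric peak static acoustic admittance at 226 Hz"; in the second, "the dependent variable will be wideband absorbance at ambient pressure averaged across half-octaves from 250 to 8000 Hz". The third is the secondary analysis of transient-evoked otoacoustic emission (TEOAE) signal-to-noise ratio.

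The text mentions no Welch or other unequal-variance version, no check of variances and no transformation for any of the three.

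On the groups, the Protocol (Methods, Subjects) says "Data will be acquired from three groups of subjects with normal hearing, sensorineural hearing loss (SNHL), and middle ear disorders", without sizes or a ratio. Its description of Aim 1 refers to "disorders common in Veterans including tympanic membrane perforation and serous otitis media", so the ME group is expected to contain more than one condition.

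**The concern.** The classical F test divides the between-group variation by one error variance pooled over all groups. If one group is more variable than the rest, that pooled figure is wrong for every comparison. It is too small for comparisons involving the variable group when that group is small, and too large for comparisons among the others.

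A group assembled from different disorders is a natural candidate for a wider spread, and the plan leaves its relative size open. Bonferroni adjusts for the number of comparisons, not for a wrong standard error. At stake is the calibration of the p-values for the two primary group comparisons and for TEOAE.

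**Working it through.** **Inputs.** From the documents: three groups, ANOVA, Bonferroni. Not in the documents and therefore assumed: two-sided alpha of 0.05; group sizes from an ME group one quarter the size of the others to one twice their size; ME SD of 1, 1.5 or 2 times a common SD of 1 in the normal-hearing (NH) and sensorineural (SNHL) groups. The plan states no error rate, power or sample size, so there is no figure of its own to reproduce.

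**Is an SD ratio of 1.5 to 2 plausible?** Suppose ME is an equal mix of two disorders, each with SD 1, whose means lie d apart. The group SD is √(1 + d²/4), which is 1.41 at d = 2 and 1.80 at d = 3. Pooling disorders can produce such ratios, but only if the disorders differ substantially on the measure. The documents do not say whether they do.

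**Overall test.** Classical: F = [Σnᵢ(mᵢ − m)²/(k − 1)] / MSE, with MSE = Σ(nᵢ − 1)sᵢ²/(N − k). Welch instead weights each group by nᵢ/sᵢ² and adjusts the denominator degrees of freedom. Type I error with equal true means, normal data and 40,000 simulated trials per setting (Monte Carlo SE about √(0.05 × 0.95/40,000) = 0.001):

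| n (NH, SNHL, ME) | Classical, SD ratio 1 | 1.5 | 2 | Welch, all three ratios |
|---|---|---|---|---|
| 40, 40, 40 | 0.049 | 0.055 | 0.059 | 0.049–0.051 |
| 50, 50, 40 | 0.050 | 0.065 | 0.078 | 0.051–0.052 |
| 50, 50, 25 | 0.050 | 0.088 | 0.120 | 0.050–0.052 |
| 50, 50, 20 | 0.050 | 0.093 | 0.141 | 0.051 |
| 60, 60, 15 | 0.051 | 0.113 | 0.181 | 0.049–0.051 |
| 30, 30, 60 | 0.050 | 0.026 | 0.021 | 0.048–0.050 |

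At (60, 60, 20) with SD ratio 2 the classical figure is about 0.155. A bimodal ME group gives almost the same results as a normal one.

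**Pairwise tests with the pooled error.** At SD ratio 2 the expected MSE and the variances it implies can be worked by hand:

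- (40, 40, 40): MSE = (39 + 39 + 39 × 4)/117 = 2.00. NH vs ME: true variance 1/40 + 4/40 = 0.125, pooled 2.00 × (2/40) = 0.100, ratio 0.80. NH vs SNHL: true 0.050, pooled 0.100, ratio 2.00.
- (50, 50, 25): MSE = (49 + 49 + 24 × 4)/122 = 1.59. NH vs ME: true 1/50 + 4/25 = 0.180, pooled 1.59 × 0.06 = 0.095, ratio 0.53. NH vs SNHL: ratio 1.59.
- (30, 30, 60): MSE = (29 + 29 + 59 × 4)/117 = 2.51. NH vs ME: true 1/30 + 4/60 = 0.100, pooled 2.51 × 0.05 = 0.126, ratio 1.26. NH vs SNHL: ratio 2.51.

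A ratio below 1 means too many false positives; above 1 means lost power. Simulation at the Bonferroni level 0.05/3 = 0.0167, SD ratio 2, agrees. Power is for a true NH–SNHL difference of 0.7 SD:

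| n | NH vs ME error, pooled | NH vs SNHL power, pooled | NH vs SNHL power, Welch |
|---|---|---|---|
| 40, 40, 40 | 0.032 | 39% | 75% |
| 50, 50, 25 | 0.081 | 67% | 85% |
| 30, 30, 60 | 0.008 | 14% | 60% |

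Welch pairwise error is 0.016 to 0.017 throughout.

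**Where Welch falls short.** With a strongly skewed (lognormal) ME group and SD ratios of 1 to 3, Welch's overall error is 0.059–0.076 at (40, 40, 40), 0.069–0.088 at (50, 50, 25) and 0.085–0.102 at (60, 60, 15). At (60, 60, 15) with equal SDs it is worse than the classical test, 0.085 against 0.045.

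**The case against.** The strongest reply is that the documents establish neither condition for inflation. A reader might infer that a small ME group is enough by itself. It is not: with equal SDs, (50, 50, 20) gives 0.050. A reader might also infer that the planned F test is known to run at two to three times its nominal level. That needs ME to be both clearly smaller and clearly more variable, and no size or SD is given. If ME is larger, the overall test is conservative. This stands, and it makes the concern conditional.

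Three further points have weight:

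- Inflation of the overall test is computed when all three means are equal. For a middle-ear test that compares healthy with diseased middle ears, this is an unlikely state. The pairwise distortion, including lost power for NH vs SNHL, does not depend on that state.
- The equal-variance reading, and the use of the pooled error for pairwise tests, are inferred from an unqualified method name. If each pairwise test used only its own two groups, NH vs SNHL would be untouched by the ME spread. The SAP does not say which applies.
- The argument for a wider ME spread comes from pooling middle-ear disorders. It is made for admittance and absorbance; nothing in the documents shows that ME is the most variable group on TEOAE.

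It might also be said that preferring Welch is generic advice. Here the mixed group and the open sizes give it a specific reason.

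**Conclusion.** The point holds as a conditional one. The SAP leaves the variance assumption unaddressed for two primary comparisons and one secondary, in a design where one group is a mixture and sizes are not fixed. Assuming an ME SD 1.5 to 2 times the others and roughly normal or bimodal data, the classical test's error is about 9% to 16% with ME at half to one third of the other groups' size (up to 18% at one quarter), 5% to 6% at equal sizes, and 2% to 3% with ME at twice their size. Under pooled-error pairwise testing, NH vs ME is anti-conservative when ME is equal or smaller in size, and NH vs SNHL loses power in all three patterns.

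Two stronger readings should be resisted. One is that Aim 1 is undermined. The Protocol frames Aim 1 as a comparison of sensitivity and specificity between test batteries, which these tests of group means do not estimate. The other is that Welch's test is valid whatever the data; the skewed cases show that it is not.

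**What to change.** In the first paragraph of the SAP, replace the unqualified method with Welch's ANOVA for all three group comparisons. Specify unequal-variance pairwise tests: either Games-Howell, or Welch t-tests with the Bonferroni adjustment already planned (or Holm). Changing only the overall test would leave the pairwise problem in place. Add a sensitivity analysis on a transformed scale, with the transformation named in advance, to be reported if the ME data are strongly skewed.

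The cost is a sentence or two and a software option. If variances are in fact equal, the power loss is about one point (76.0% against 75.3% for NH vs SNHL at n = 40 per group, and at most about 1.5 points in the size patterns tried). The remaining weakness is a small, strongly skewed ME group, where Welch protects incompletely and can do worse than the classical test. The transformed-scale analysis is there for that case.

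### Holm's step-down correction would replace Bonferroni at almost no cost and never reject fewer group comparisons; an optional efficiency gain, not an error in the plan

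*SAP*

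**What the plan says.** The first paragraph of the Statistical Analysis Plan section sets out ANOVAs across the normal-hearing (NH), sensorineural (SNHL) and middle-ear (ME) groups, and continues: "Bonferroni corrections will be applied for multiple comparisons". The next sentence adds a second kind of test: "T-tests will be used to examine effects of method (clinical vs. experimental wideband) within each subject group".

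For the primary outcome, "separate ANOVAs will be used to examine differences across groups within each method". That makes two ANOVAs, one on 226 Hz peak static admittance and one on ambient-pressure wideband absorbance. A further ANOVA on TEOAE signal-to-noise ratio is secondary. The three-group design is also in the Protocol (Methods, Subjects): "Data will be acquired from three groups of subjects with normal hearing, sensorineural hearing loss (SNHL), and middle ear disorders".

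The available text does not say which tests form a family for the correction, and gives no alpha, sidedness, group size or effect size. Part of the SAP was not available for this review, so the missing figures are treated here as unknown, not as omissions.

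**The concern.** Three groups give three pairwise contrasts per ANOVA. Single-step Bonferroni holds every contrast to the strictest threshold, even after another contrast in the same family has been rejected. Holm relaxes the threshold after each rejection and keeps the same family-wise guarantee.

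This is relevant because the Protocol's goal is differential diagnosis, which depends on separating particular pairs of groups and not only on showing that some group differs. If the most distant pair is easy to detect, the remaining pairs are where Bonferroni loses power.

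**Working it through.** **Inputs.** From the SAP: three groups and Bonferroni correction. Inferred from the position of the sentence: the family is the m = 3 pairwise contrasts within one ANOVA. Assumed, because the available text gives no values: two-sided alpha 0.05, 20 to 60 subjects per group, normal data with equal variances, and group means in SD units. The plan has no power or error figure of its own to reproduce.

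**Thresholds.** Order the p-values p(1) ≤ p(2) ≤ p(3).
- Bonferroni: 0.05/3 = 0.0167 for each.
- Holm: 0.05/3 = 0.0167, then 0.05/2 = 0.025, then 0.05/1 = 0.05, stopping at the first failure.

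Every Holm threshold is at least as large as Bonferroni's, so Holm rejects whatever Bonferroni rejects. The first step is the same test, so the chance of at least one rejection is identical.

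**Error bound.** Suppose m0 of the contrasts are truly null. When Holm first rejects a true null, at most m − m0 contrasts have been rejected before it, so the threshold in force is at most alpha/m0. By the Bonferroni inequality the family-wise error is at most m0 × alpha/m0 = alpha, whatever the dependence. With three groups, m0 can be 3 or 1:
- All means equal (m0 = 3): the two methods have the same error. Simulation gave 4.3% to 4.5% for both.
- One pair equal (m0 = 1): Bonferroni is limited to 0.05/3 = 1.7% and Holm to 0.05/1 = 5%. Simulation with means 0/0/1.2 SD and 30 per group gave 1.7% and 4.9%.

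**Power.** Simulated with pooled-variance t-tests, 40,000 runs per setting:

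| Means (SD) | n per group | Contrast | Bonferroni | Holm | Gain (points) |
|---|---|---|---|---|---|
| 0/0.5/1.0 | 20 | each 0.5 SD pair | 20% | 25% | about 5 |
| 0/0.5/1.0 | 30 | each 0.5 SD pair | 31% | 40% | about 9 |
| 0/0.5/1.0 | 30 | 1.0 SD pair | 92.1% | 92.4% | 0.3 |
| 0/0.5/1.0 | 60 | each 0.5 SD pair | 63% | 76% | about 13 |
| 0/0.7/1.2 | 30 | 0.7 SD pair | 61% | 71% | 10 |
| 0/0.7/1.2 | 30 | 0.5 SD pair | 31% | 44% | 13 |
| 0/0/0.8 | 30 | each true difference | 74.5% | 77.5% | 3 |
| 0/0/1.2 | 30 | each true difference | 98.6% | about 99% | under 1 |

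For 0/0.5/1.0 the chance of at least one significant pair is the same under both methods: 77.5%, 92.9% and 99.9% at 20, 30 and 60 per group. The chance that all three pairs are significant rises from 4% to 14% at 30 per group, and from 32% to 56% at 60.

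**The case against.** Bonferroni is valid, holds family-wise error under any dependence, and conflicts with nothing in either document. A reader might infer that the plan's error control is wrong or that a stated result would change; neither follows. This stands, and it makes the point an efficiency suggestion only.

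A reader might also carry the gains of 9 to 13 points over to the primary outcome. The documents do not support that. The Protocol's opening paragraph assigns absorbance to middle-ear assessment and otoacoustic emissions to cochlear assessment. For the two primary measures it is therefore plausible that NH and SNHL are similar and only ME differs. In that pattern the gain is about 0 to 3 points.

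Nor is power given up for nothing. Bonferroni has simple matching simultaneous intervals. Any pair that Holm rejects and Bonferroni does not has p above 0.0167, so its 98.33% interval contains zero. Bonferroni also gives the lower false-positive rate when exactly one pair is truly equal. Both costs stand, though the SAP specifies no confidence intervals and Holm stays within the 5% limit.

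Finally, Holm is not the most powerful choice for three groups. Pairwise tests at 0.05, done only if the ANOVA F-test is significant, kept simulated family-wise error at about 5% and gave 48% power for a 0.5 SD pair (means 0/0.5/1.0, 30 per group), against 40% for Holm and 31% for Bonferroni. That is a fair alternative for the sponsor to weigh, but it does not favour Bonferroni.

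**Conclusion.** The point holds as a cheap, optional improvement. The direction of the gain is a mathematical fact: Holm never rejects fewer contrasts and has the same family-wise bound. Its size is illustrative and rests on assumed alpha, group sizes and effects, and on reading the family as three contrasts per ANOVA. It is material only if all three group means differ. It is small if one group stands apart, and absent for the question of whether any pair differs. A larger family, for example one pooling both primary ANOVAs, would change the thresholds and the figures. The undefined family matters at least as much as the choice of method, since neither correction can be applied until it is settled.

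**What to change.** Keep the scope of the sentence and change the method, for example: *Holm-Bonferroni corrections will be applied for multiple comparisons; for group comparisons the family is the three pairwise contrasts within each ANOVA.* Defining the family by ANOVA and not by outcome avoids ambiguity, because the primary outcome has two ANOVAs and could otherwise be read as six contrasts. Keeping the general first clause avoids removing correction from other tests that the present sentence may cover. The SAP should also state alpha, unless it is given elsewhere, and say whether the clinical-versus-wideband t-tests are corrected and in what family.

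The cost is one revised sentence and one software option. If simultaneous confidence intervals are reported, add a note that they may include zero for a pair that Holm declares significant. The change should be made only if group results have not yet been examined; otherwise keep Bonferroni as planned and label any Holm results as supplementary.

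### The study asks which test method is more accurate, but the SAP plans only comparisons of means, so the stated hypothesis goes untested

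*SAP*

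**What the plan says.** The protocol states its objectives in terms of accuracy:

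- Aim 1 concerns "comparing the sensitivity and specificity of the WB battery to the traditional immittance battery for disorders common in Veterans".
- Aim 3, on otoacoustic emissions, is to "evaluate their test performance in classifying ears with normal hearing and sensorineural hearing loss".
- Across the aims, the protocol intends to examine "the diagnostic accuracy of the full WB test battery in comparison to the single-frequency admittance test battery to detect any type of hearing loss".
- "The hypothesis is that the WB test battery is more accurate than the traditional immittance test battery", in identifying ears with normal status and ears at risk of pathology.

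On design, the Methods section says "Data will be acquired from three groups of subjects with normal hearing, sensorineural hearing loss (SNHL), and middle ear disorders" and, under Testing, "All subjects will receive the same clinical and WB test battery".

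The SAP's opening paragraph plans ANOVAs across the three groups, Bonferroni correction, and t-tests of method within each group. It then takes the outcomes in turn. For the primary Middle Ear Test, "separate ANOVAs will be used to examine differences across groups within each method": one ANOVA on peak admittance at 226 Hz and another on averaged ambient absorbance. For the reflex outcome, within-group t-tests compare the clinical and WB thresholds. For the emission outcome, one ANOVA compares mean TEOAE signal-to-noise ratio across groups.

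**The concern.** Sensitivity, specificity and AUC describe how well a measurement sorts individuals by disease status. An ANOVA asks whether group means differ, and a group mean can differ reliably on a measure that classifies poorly. The hypothesis is also comparative, while the two primary ANOVAs are run separately and no contrast links them.

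Two outcomes invite misreading. If both ANOVAs are significant, nothing ranks the methods. If only one is, the temptation is to call that method better, although a significant and a non-significant result are not evidence of a difference between them.

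If an accuracy analysis is added once the data are in hand, the cut-off, the score and the comparison group are all open to choice at a point when the answer can be seen.

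**Working it through.** **Matching objectives to analyses**

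| Protocol objective | Needs | SAP provides |
|---|---|---|
| Aim 1: sensitivity and specificity, WB v immittance | Both measures set against middle-ear status, and a between-method comparison | Two separate ANOVAs of means |
| Aim 2: reflex threshold, WB v clinical | Within-subject comparison of thresholds | Within-group t-tests: served |
| Aim 3: classifying normal v SNHL ears (TEOAE and spontaneous emissions) | Sensitivity, specificity or AUC | ANOVA of mean TEOAE signal-to-noise ratio; spontaneous emissions absent |
| Full battery v single-frequency battery | A combined score or rule for each, and a comparison | Nothing |

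Two features of the SAP might seem to fill the gap.

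- *Bonferroni correction.* The SAP does not say what it applies to. If it covers pairwise group contrasts, a middle-ear (ME) v normal-hearing (NH) contrast still lies inside one method.
- *Within-group t-tests of method.* For the middle-ear outcome these would set admittance against absorbance, which are different quantities, inside one group. Accuracy needs diseased and non-diseased subjects together.

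**Illustration of size**

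The SAP has no figure to reproduce. Assumptions: three equal groups of n; normal measures with SD 1; only ME shifted, by d; the two measures correlated within subject. Then AUC = Φ(d/√2), and sensitivity at 90% specificity = Φ(d − 1.2816).

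- d = 1.0: AUC = Φ(0.707) = 0.76; sensitivity = Φ(−0.28) = 39%.
- d = 1.5: AUC = Φ(1.061) = 0.86; sensitivity = Φ(0.22) = 59%.

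*Accuracy truly different (d = 1.0 v 1.5, correlation 0.5), simulated:*

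| n per group | 20 | 30 | 50 | 80 |
|---|---|---|---|---|
| Both omnibus ANOVAs significant (0.05) | 90% | 98% | 100% | 100% |
| Both ME v NH contrasts significant (0.05/3) | 75% | 92% | 99% | 100% |

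*Accuracy truly equal, exactly one method significant (correlation 0.3 to 0.6):*

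| n per group | 20 | 30 | 50 | 80 |
|---|---|---|---|---|
| Omnibus, d = 0.5 | 29–37% | 31–42% | 25–33% | 11–14% |
| Omnibus, d = 0.7 | 30–40% | 21–28% | 6–8% | 0.5% |
| Omnibus, d = 1.0 | 12–16% | 3% | 0.1% | 0% |
| ME v NH contrast, d = 0.5 | 21–27% | 27–35% | 30–40% | 22–30% |
| ME v NH contrast, d = 0.7 | 29–40% | 29–39% | 16–21% | 4% |
| ME v NH contrast, d = 1.0 | 23–31% | 10–13% | 1% | 0% |

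Pairwise contrasts therefore do not remove the problem.

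**What a direct comparison could deliver**

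Paired DeLong test under the first scenario (true AUC difference 0.856 − 0.760 = 0.096):

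| n per group | 20 | 30 | 50 | 80 |
|---|---|---|---|---|
| ME v all non-ME: power | 32% | 46% | 70% | 88% |
| ME v all non-ME: 95% CI half-width | 0.12 | 0.10 | 0.08 | 0.06 |
| ME v NH only: power | 25% | 36% | 55% | 77% |
| ME v NH only: 95% CI half-width | 0.15 | 0.12 | 0.09 | 0.07 |

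For sensitivity at 90% specificity (true difference 0.586 − 0.389 ≈ 0.20), 1.96 × SD of the estimated difference, ME v all non-ME, is 0.25, 0.21, 0.16 and 0.13 with a cut-off fixed in advance. It is about 0.35, 0.28, 0.22 and 0.17 when the cut-off is estimated from the non-ME subjects.

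Ignoring that estimation matters. With equal accuracy (d = 1.0, n = 30 and 80), an exact McNemar test at estimated cut-offs rejects in about 8–12% of trials (all non-ME) or 16–20% (NH only), against 2–3% with fixed cut-offs.

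**The case against.** The SAP never says that one significant and one non-significant ANOVA will be read as a difference in accuracy, so the second simulation measures a misuse that the plan does not announce. That is fair. The defect is the absent comparison, and it needs no simulation.

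The simulated rates also depend heavily on assumed inputs. At d = 1.0 the one-significant pattern falls to 3% at 30 per group for the omnibus test. The highest rates at larger n come from d = 0.5, which is a weak test (AUC 0.64). The model treats SNHL as identical to NH on both middle-ear measures and gives ME one uniform shift, although Aim 1 names at least two middle-ear disorders. The figures should be read as illustration only.

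One passage of the SAP was not in the text supplied for review, and an accuracy analysis could in principle be there. The remaining text nevertheless reads as a complete plan: general methods, then the primary and both secondary outcomes.

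The ANOVAs do carry indirect information, because better group separation generally goes with better classification. They still neither estimate accuracy nor test the stated comparison. Aim 2 is properly served, so the failure is not plan-wide.

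**Conclusion.** The concern holds, and the SAP must be changed before it is used. Carried out exactly, the SAP text reviewed gives no estimate of sensitivity, specificity or classification performance and no test of the protocol's hypothesis. This follows from the wording and depends on no assumed number.

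In practice, where the methods truly differ and both separate the groups well, the likely result is two significant ANOVAs that cannot be ranked (90% of trials or more from 20 per group, at AUCs of 0.76 and 0.86). Where they do not differ, discordant significance ranges from negligible to about 40%, depending on effect size, group size and correlation, none of which the documents give.

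**What to change.** **Needed in the SAP**

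1. *Aim 1.* A paired comparison of the two middle-ear methods in subjects who receive both batteries: the difference in AUC (DeLong is one suitable method), or in sensitivity and specificity at a pre-specified cut-off or score, with 95% confidence intervals.
2. *Cut-offs.* Fix them in advance, or carry their uncertainty into the interval, for example with a bootstrap by subject that re-estimates them.
3. *Comparison group.* State whether it is NH or all non-ME subjects.
4. *Unit of analysis.* State whether it is the ear or the subject, and cluster by subject if both ears contribute.
5. *Reference standard.* Define middle-ear status from information independent of both index tests.
6. *Aim 3.* Sensitivity, specificity or AUC with 95% confidence intervals for TEOAE signal-to-noise ratio in normal v SNHL ears. Do the same for spontaneous emissions, or state why they are left out.
7. *Full battery.* List the component tests of each battery and pre-specify a comparison of accuracy that guards against overfitting, such as cross-validation.

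The lead measure and any fixed specificity are the sponsor's choice. The ANOVAs can stay as supporting analyses.

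**Cost**

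Mainly SAP text and analysis time, because paired testing is already planned. There are two downsides.

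- *Precision.* At an assumed 30 to 50 per group, power for the AUC difference is about 36–70% across the two comparison groups, so the result should be reported as an estimate with its interval.
- *Source of the diagnosis.* The text does not say how middle-ear status is set. The Methods plan otoscopy and air- and bone-conduction audiometry but do not say whether these suffice. If the label comes from the earlier VA hearing evaluation, it may rest partly on the comparator, which the protocol calls a "standard single-frequency clinical immittance test battery routinely used in the assessment of auditory function in Veterans". Another source might then be needed.
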